It is clear that there is a pressing need for research into if, why and for whom internet-based interventions work. Qualitative research has highlighted several potential benefits of internet-based interventions that require further research [19, 21]. These outcomes were mostly related to aggression regulation, since this is an important and large part of outpatient treatment. In general, therapists did see multiple advantages, but indicated that they did not expect any major improvements due to these interventions: they were mostly expected to slightly bolster the effectiveness of existing treatment, mostly by providing patients with more tools to work on their treatment independently. Because of this, changes might be attributed to the patient's own effort as opposed to that of the therapist, which could benefit **self-efficacy** towards behaviour change. Additionally, internet-based interventions offer multiple ways of acquiring knowledge and skills that are tailored to the target group, such as multi-media, written assignments and peer-stories. This is done to accommodate different types of learning that better fit the patient than face-to-face treatment sessions and can thus also increase the patient's confidence in regulating their aggression. Furthermore, therapists also expected that these intervention can positively affect **treatment readiness** of patients because they can support the patient in gaining insight into their problems and defining their own goals. Being responsible for their own treatment by working on an internet-based intervention individually, and gaining more insight into their own behaviour, might influence their sense of ownership and motivation to work on their treatment. Therapists, patients and researchers expect that this potential increase in self-efficacy and treatment readiness could facilitate actual behaviour change: **aggression** might decrease due to the independence, knowledge, insights and skills that are acquired by means of these interventions [17]. This can result in decreased risk for recidivism, reflected in an improved score on **risk assessment instruments**. Finally, it is also expect that, if used well, these

interventions might result in more **efficient treatment** because part of face-to-face treatment can be replaced by the internet-based intervention [21, 27]. However, for all of these expectations goes that they are based on qualitative research.

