#### 4.4 Sample size calculation

This sample size calculation is conservatively based on the ability to detect at least a moderate effect of Cohen's  $d = .50$  on the primary outcomes at follow-up (T3). A power analysis was conducted with G\*power. The analysis was conducted with a moderate effect size of 0.5, a  $\beta$ -power of .8, a p-value of 5%, and an independent two-sided t-test as method of analysis. This analysis showed that 64 patients need to be included in each condition. This means that a total of 128 patients needs to be included. Accounting for a drop-out of 20%, the goal for inclusion is set at a total of 154 patients. It is important to note that participants in the experimental condition are considered as a 'drop-out' when they don't fill out the questionnaires at all measuring moments, not when they stop using the intervention. In other words: patients can stop using the intervention. In other words: patients can stop using the intervention, but can still complete their participation in the study if they fill out all questionnaires. Adherence to the intervention is not the same as drop-out from the study, since it is a different concept. The main reason for this is that earlier research has shown that patients often stop using these interventions before all lessons are completed, so it is not realistic to expect that all patients fully complete the intervention. In order to account for this, the number of completed lessons will be included as a moderator for effectiveness in the analyses to investigate whether adherence is related to effectiveness. Additionally, a sub-goal of this study is to determine whether engagement is a predictor of adherence and effectiveness to incorporate non-adherence to the intervention in the study. The intended 154 patients will be included at four different organizations that all have multiple forensic outpatient clinics.

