## 10. STATISTICAL ANALYSIS

### 10.1 Primary study parameter(s)

Data will be analysed using IBM SPSS software (version 24.0) and significance was accepted at 0.05 or lower. Analyses will be done on intention to treat (ITT) basis.

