#### ***Determining effectiveness***

In order to determine whether the internet-based intervention Aggression is effective, multiple scenarios are possible.

First of all, it is possible that the scores of the experimental groups do not increase more than those of the control group on all three primary outcome measures at all measurement points (T1, T2 and T3). In that case, the intervention is viewed as ineffective. Second, there might be a significant improvement of the experimental group compared to the control group on one or more of the outcome measures on T1 (so halfway the intervention), but not on T2 and T3. This indicates that the intervention shows some promise, but cannot be viewed as effective. Further research on why the effects are not maintained until the end of the intervention and on the long term is then warranted. These questions will be partly answered by means of the interviews at T3. Third, there might be a change on T2 - so directly after completing the intervention - on one or more of the outcome measures in the experimental group compared to the control group, which is not maintained at T3. In that case, the intervention is viewed as promising and potentially useful for clinical practice because participants did experience benefits, but not effective because the effects are not maintained on the long term. In that case, future research into why these effects are not maintained and what this means for the usefulness of these interventions in forensic outpatient care is necessary. Fourth, there might be an improvement of the experimental group compared to

the control group on T3 on one or two outcome measures. In that case, the intervention is viewed as effective since it leads to benefits on the long term. However, future research is again warranted to investigate why these changes did not occur on the other outcome measure(s). Finally, if the experimental group outperforms the control group on all three outcome measures at T3, the conclusion will be that the intervention is effective and no future research is warranted. However, this of course does not mean that future research is not desirable for the sake of replicability.

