A more abstract, indirect benefit – especially relevant for participating therapists - is that this study can contribute to better forensic mental healthcare. The importance of this study is illustrated by a recent study amongst Dutch forensic mental healthcare professionals, which clearly showed the need for more robust evaluation studies of eHealth interventions [19]. Especially considering the fact that internet-based interventions have been present in Dutch forensic mental healthcare for about ten years, is quite surprising that their effectiveness has not been studied yet. Consequently, it is essential to study the effectiveness of these modules, especially in a domain in which evidence-based practice is a core value. If the web-based interventions prove to be effective, this can be an additional impulse for implementation in clinical practice. In that way, these modules provide an effective way to provide additional care to vulnerable patients, which might reduce the overall changes of recidivism and quality of care. In line with this, the effectiveness of these interventions might provide an additional impulse for implementation, since professionals working in forensic mental healthcare indicate that the absence of evidence is one of the experienced implementation barriers [19, 21]. If this study shows no proof for effectiveness, this should be a starting point for a broader discussion in forensic mental healthcare: is it worthwhile to invest much time, money and other resources in the implementation of these modules, or should these resources be focused on other, more promising technological additions to care? In any case, this study will contribute to evidence-based practice and thus the most optimal form of treatment for forensic psychiatric outpatients.

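### The 'ineffective' label reads non-significance on all nine comparisons as no effect, although the trial cannot exclude a small benefit

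*Combined protocol and SAP*

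**What the plan says.** The first scenario under Determining effectiveness (section 10.1) covers scores in the experimental group that "do not increase more than those of the control group on all three primary outcome measures at all measurement points (T1, T2 and T3"). It concludes: "In that case, the intervention is viewed as ineffective". The word significant is absent there. It appears in the second scenario, where "there might be a significant improvement of the experimental group compared to the control group", and section 10.1 opens with the threshold: "significance was accepted at 0.05 or lower". The same section adds Bonferroni-corrected post-hoc t-tests but does not say how many tests form the family.

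Section 4.4 sizes the trial for d = 0.5 at T3, with "a p-value of 5%, and an independent two-sided t-test as method of analysis", 80% power and 64 patients per arm. The introduction reports what therapists expected of these modules: "they were mostly expected to slightly bolster the effectiveness of existing treatment". It attaches no figure to that. Section 11.4.1 describes a null result more carefully: "If this study shows no proof for effectiveness, this should be a starting point for a broader discussion in forensic mental healthcare".

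Section 10 sets no confidence-interval criterion, no margin and no category for an inconclusive result.

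**The concern.** Failing to show a difference is not the same as showing that there is none. A trial of this size can leave a small benefit undetected, and a small benefit is what the therapists cited in the introduction anticipated. Under the rule such a benefit would be reported as ineffectiveness, with nothing to show the reader how large an effect the data still allow. Section 11.4.1 makes a null result the start of a discussion about whether to keep investing in these modules, so the label is likely to be used.

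The scenarios also treat results unevenly. Those with mixed findings call for further research. The wholly null one does not, although it is the one in which imprecision matters most.

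**Working it through.** **Inputs from the documents.** d = 0.5, two-sided alpha 0.05, power 0.80, 64 per arm, 20% dropout and 154 enrolled (section 4.4); three outcomes at T1, T2 and T3, so nine comparisons (section 10.1).

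**Assumptions.** Slight = d of 0.2 to 0.3. Correlation 0.3 to 0.7 between outcomes and 0.5 to 0.8 between visits. Baseline correlation 0.5 to 0.7 where adjustment is considered.

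**1. The plan's own figure.** The noncentrality is 0.5 × √(64/2) = 2.83 on 126 degrees of freedom, which gives power 0.801. The 64 per arm is reproduced. Enrolment is 128 × 1.2 = 153.6, so 154. After 20% dropout, 154 × 0.8 = 123.2, so about 123 complete (61 and 62).

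**2. Power of one T3 t-test at 61/62.** In SD units the standard error is √(1/61 + 1/62) = 0.180.

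- d = 0.2: 0.2/0.180 = 1.11, power 20%.
- d = 0.3: 0.3/0.180 = 1.66, power 38%.
- d = 0.5: 0.5/0.180 = 2.77, power 78.5%.

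Baseline adjustment multiplies the standard error by √(1 − r²), which is 0.866 at r = 0.5 and 0.714 at r = 0.7. Power over d = 0.2 to 0.3 then runs from about 25% (d = 0.2, r = 0.5) to about 64% (d = 0.3, r = 0.7).

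**3. The full nine-comparison rule.** Nine test statistics were simulated as multivariate normal, each with mean d/0.180. The result counts as ineffective when none is significant in favour of the intervention. The ranges span the assumed correlations.

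| True d on all nine | Unadjusted | Three-fold Bonferroni | Nine-fold Bonferroni |
|---|---|---|---|
| 0.2 | 30–51% | 55–71% | 72–83% |
| 0.3 | 10–28% | 26–47% | 44–63% |
| 0.5 | 0.2–3% | 1–9% | 4–17% |

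The three-fold column uses t critical values; using t rather than normal values moves any entry by at most about 3 points. Three-fold and nine-fold are both assumptions, because section 10.1 does not define the family.

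**4. Only one outcome responds.** At one assumed pair of correlations (0.4 between outcomes, 0.6 between visits), with the effect on a single outcome at all three visits:

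- d = 0.3: ineffective in 38% of trials unadjusted and 73% with nine-fold Bonferroni.
- d = 0.5: 7% and 28%.

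This case is realistic. Section 8.1 says it is not known which outcome will best show change, and section 8.1.1 doubts a direct effect on aggression.

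**The case against.** Five points can be made for the plan.

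- **The sentence does not mention significance.** That is true. Taken literally, it would need all nine estimates to be no better than control. A small, non-significant positive difference would then fall under no scenario, so the passage needs rewording on either reading.
- **The main analysis is a mixed model that includes T0, not a raw t-test.** This stands. The simulated chances use no baseline information and would fall with it. Even so, power at d = 0.2 stays at about 25 to 34% with adjustment.
- **All nine comparisons must fail.** This also stands. A reader might infer that the trial would often call its own target effect ineffective: the unadjusted 95% half-width is 1.96 × 0.180 = 0.35 SD, so a non-significant estimate of 0.15 to 0.35 has an upper limit of 0.50 to 0.70. That describes one unadjusted comparison, whereas the label requires nine failures, and step 3 shows that this is rare at d = 0.5 throughout. With baseline adjustment at 64 per arm, the half-width is 0.30 to 0.25 and the largest non-significant upper limit 0.61 to 0.50.
- **The expectation of a slight gain belongs to therapists.** Correct. The protocol's own planning value is d = 0.5, and 0.2 to 0.3 is only an assumed translation.
- **No decision follows mechanically.** Section 11.4.1 proposes a discussion about investment; it does not say that resources would be withdrawn. Section 10.1 also promises nuance from post-hoc analyses, graphs and interviews. None of these is a precision criterion, and none changes the label.

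**Conclusion.** The concern holds for small effects and for an effect confined to one outcome. On the significance reading, which is inferred, a true d = 0.2 on every outcome and visit would be labelled ineffective in 30 to 51% of trials unadjusted and 72 to 83% with nine-fold Bonferroni. For d = 0.3 the figures are 10 to 28% and 44 to 63%. They rest on 61 and 62 completers, equal effects at all three visits, the assumed correlations and no baseline adjustment. If recruitment stops early, which section 8.8 allows, intervals would widen and the chances would rise.

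The concern does not extend to a true d = 0.5 on every outcome and visit: 0.2 to 3% unadjusted and 4 to 17% with nine-fold Bonferroni.

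**What to change.** - Under Determining effectiveness, replace 'ineffective' with 'no benefit demonstrated', in line with the more cautious wording of section 11.4.1. State that the scenarios refer to statistical significance, and define the Bonferroni family.
- Report the between-group difference on each outcome at T1, T2 and T3 with its 95% confidence interval from the mixed model, signed so that positive values mean benefit.
- State 'no benefit of the size the trial was designed to detect' only if the T3 upper limits for all three outcomes lie below d = 0.5. Use the model's own intervals, not a fixed cut-off such as an observed 0.15 SD, which belongs to the unadjusted t-test. Say in advance which SD converts the limits to d.

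The change is to wording and reporting only; it needs no further patients, data or tests. The price is a more cautious label in some null scenarios. Even with no true effect, 64 per arm and no baseline adjustment, at least one T3 interval would still contain 0.5 in 30 to 39% of trials without a significant T3 result, so the stronger statement would not always be available.

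### Section 10.1: scenario 3 (not effective) and scenario 4 (effective) can both apply to the same result, and no order of precedence is stated

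*Combined protocol and SAP*

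**What the plan says.** The verdict rule is in section 10.1 of the combined protocol and SAP, under Determining effectiveness. Numbered in the order given, and paraphrased except where quoted:

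- **Scenario 1:** no advantage on the outcomes at any visit. Verdict: ineffective.
- **Scenario 2:** an advantage at T1 on at least one outcome, absent at T2 and T3. Verdict: some promise, cannot be called effective.
- **Scenario 3:** a change at T2 "on one or more of the outcome measures in the experimental group compared to the control group, which is not maintained at T3". Verdict: promising, "but not effective because the effects are not maintained on the long term".
- **Scenario 4:** an advantage at T3 on one or two outcomes. "In that case, the intervention is viewed as effective since it leads to benefits on the long term".
- **Scenario 5:** an advantage at T3 on all three. Verdict: effective.

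There are three outcomes (RESE, CVTRQ, AVL-AV). Section 8.1 gives a different rule: effective requires change on all three at T3, and an advantage on at least one outcome at any of T1 to T3 makes the intervention only potentially effective.

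**The concern.** Scenario 3 is triggered by what happens to any one outcome, but its verdict covers the whole intervention. It does not require the other outcomes to be negative at T3. Scenario 4 looks only at T3 and sets no condition on T2. With three outcomes moving separately, one result can meet both.

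The trial's headline conclusion is then not fixed by its own rule for such a result. The study is unblinded with self-reported outcomes, and section 11.4.1 expects the result to inform whether to keep investing in these modules. A decision rule should not leave the choice between opposite labels open until the data have been seen.

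**Working it through.** **1. Set the scenarios against concrete results** (+ means significantly better than control)

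| Result | RESE | CVTRQ | AVL-AV | Scenario 3 | Scenario 4 | Section 8.1 |
|---|---|---|---|---|---|---|
| A | + at T2, not at T3 | + at T3 | never + | met: not effective | met: effective | potentially effective |
| B | + at T2, not at T3 | + at T3 | + at T3 | met: not effective | met: effective | potentially effective |

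An outcome that is positive at T2 only is by definition not positive at T3. So at most two outcomes can then be positive at T3, and every clash involving scenario 3 is with scenario 4, never with scenario 5. Replacing T2 by T1 in result A (RESE positive at T1 only) meets scenarios 2 and 4 together.

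**2. Reproduce the plan's sample size.** Section 4.4 gives: "The analysis was conducted with a moderate effect size of 0.5"; "a p-value of 5%, and an independent two-sided t-test as method of analysis"; power 0.80; "This analysis showed that 64 patients need to be included in each condition".

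- Normal approximation: n = 2(1.960 + 0.842)²/0.5² = 62.8, so 63 per arm.
- t-test solution: 63.77, so 64 per arm. Power at 64 is 0.801. The plan's 64 reproduces.
- 128 × 1.2 = 153.6, so 154, as stated.

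**3. Frequency of the clash.** The documents give none, so this is a simulation with stated assumptions.

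- Inputs from the documents: 64 per arm, three outcomes, and the 5% level (section 10.1: "significance was accepted at 0.05 or lower").
- Assumed: the true effect at T2 and on each outcome; T2-T3 correlation 0.5 to 0.7; between-outcome correlation 0.3 to 0.5; *not maintained* taken as non-significant at T3; no multiplicity correction.
- Model: six correlated z-statistics (three outcomes at T2 and T3), each with mean d × √(64/2). At d = 0.5 this is 0.5 × 5.657 = 2.83. An outcome is positive if z > 1.96.
- Clash: at least one outcome positive at T2 and not at T3, and at least one outcome positive at T3.

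| True effect | Probability that scenarios 3 and 4 both apply |
|---|---|
| None | about 0.5% |
| d = 0.2, all three outcomes, sustained | 8 to 10% |
| d = 0.3, all three, sustained | 16 to 22% |
| d = 0.4, all three, sustained | 20 to 29% |
| d = 0.5, all three, sustained | 17 to 25% |
| d = 0.5, one outcome only, sustained | about 3% |
| d = 0.5 at T2 fading to 0.3 at T3, all three | 40 to 49% |

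At a sustained d = 0.5, about 50 to 64% of the trials that land in scenario 4 also meet scenario 3.

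**4. Sensitivity**

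- Wider correlations (between outcomes 0 to 0.7, T2-T3 0.3 to 0.8): 12 to 34% at a sustained d = 0.5 on all three outcomes.
- Bonferroni: section 10.1 names it for the post-hoc tests without defining the family. At 0.05/3 per test the figures for all three outcomes are 20 to 29% at d = 0.5, 10 to 13% at d = 0.3 and about 4% at d = 0.2. A correction shifts the frequency and does not remove the clash.
- Scenario 2 was not simulated. Its overlap is shown by the wording alone.

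**The case against.** The best defence is that the list is a ladder ordered by the latest visit with a benefit: none, T1, T2, T3 on some outcomes, T3 on all. Each verdict carries a reason that fits this. Scenario 3 fails because nothing lasts, and scenario 4 succeeds because something does. Scenario 4 even foresees outcomes that do not improve at T3, since it asks for research into why they did not. In result A the intervention does have a T3 benefit, so scenario 4's reason holds and scenario 3's does not hold for the intervention as a whole. This is very probably the intent, and it shows which way to fix the text. It is not written down, however. Taking the scenarios in listed order would stop at scenario 3 and give the opposite headline. The closing paragraph of the section promises a closer look at timing, plus interviews, but no precedence rule.

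A reader might infer that some fixed share of trials with a real effect, such as 15 to 30%, would receive two opposite verdicts. The documents do not support this. The range fits a sustained moderate effect on all three outcomes. Section 8.1.1 says a direct effect on aggression may be too much to expect, and section 1 reports that therapists expected only a slight gain. If one outcome responds, the figure is about 3%; if the effect fades, it is well above 30%. Also, with equal true effects at T2 and T3, most counted cases are effects that persisted but missed significance at T3. That treatment of *not maintained* is an assumption, because the plan does not define the term.

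A reader might also infer extra false claims of benefit. With no effect the clash occurs in about 0.5% of trials, so this is a problem of an ambiguous verdict and not of the error rate.

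**Conclusion.** The point holds as a defect of wording. As written, scenarios 3 and 4 are not mutually exclusive, their verdicts are opposite and no precedence is given; scenario 2 has the same weakness. This follows from the text and needs no simulation.

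The frequency rests entirely on assumptions about the T2 effect, the number of outcomes affected, the correlations and the meaning of *not maintained*. Plausible settings run from about 3% to almost 50%. The plan's own planning effect gives about 17 to 25%, if it is taken to hold on all three outcomes and equally at T2 and T3. No single figure should be quoted without those conditions.

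Nor does the text support the view that correcting section 10.1 alone would settle the verdict. Results A and B would become effective under section 10.1 and remain only potentially effective under section 8.1.

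**What to change.** State in section 10.1 that T3 decides first, which agrees with the reasons the plan already attaches to each verdict. Then:

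- Scenario 3: *on one or more outcomes at T2, and on none of the three outcomes at T3*.
- Scenario 2: *on one or more outcomes at T1, and on none at T2 or T3*.
- If any outcome is positive at T3, scenarios 4 and 5 alone give the overall verdict. Outcomes positive only at T1 or T2 are reported outcome by outcome.

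With this wording the overlaps of scenarios 2, 3 and 4 are zero by construction, and *not maintained* no longer needs a separate definition in scenario 3.

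In the same edit, reconcile section 8.1, which reserves the effective label for change on all three outcomes at T3, with scenario 4, so that only one rule remains.

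Cost: two reworded sentences and a short precedence statement in section 10.1, plus the reconciliation with section 8.1. No data, patients or analyses change. The edit should be dated before any between-group results are seen.

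### Section 10.1 concludes that effects are 'not maintained' by comparing one visit's result with a later one, with no contrast of the group effect between those visits behind the label

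*Combined protocol and SAP*

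**What the plan says.** Section 10.1 (Research objective 1) plans a linear mixed model with group, time and their interaction over T0–T3. It adds Bonferroni-corrected post-hoc tests of the group difference and of change over time within each group. The level is given as "significance was accepted at 0.05 or lower".

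Determining effectiveness then turns visit results into verdicts. Scenario 2 is a significant advantage "on one or more of the outcome measures on T1 (so halfway the intervention), but not on T2 and T3": some promise, not effective, and research is wanted on why the effect did not last. Scenario 3 is a group difference at T2 "which is not maintained at T3. In that case, the intervention is viewed as promising and potentially useful for clinical practice", "but not effective because the effects are not maintained on the long term"; again research is wanted on the loss. Scenario 4 calls the intervention effective if one or two outcomes improve at T3, and asks why no change occurred on the rest. A closing paragraph promises nuance on when changes occur and how long they last, through post-hoc analyses, plots and interviews, but sets no criterion.

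Scenario 3 does not repeat the word significant. Scenario 2 uses it and the model section supplies tests of the group difference, so 'significant at T2, not significant at T3' is the natural reading. No other definition is given.

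**The concern.** Whether a benefit faded is a question about the difference between two group effects. The rule answers it by setting one test result beside another. A steady effect near the edge of detectability will often be significant at one visit and miss at the next by chance. Any extra loss of patients by T3 adds to this, because T3 then has less power.

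The objectives (section 2) ask about benefit on both the short and the long term, so the durability statement is among the main conclusions. Section 11.4.1 says that a finding of no effectiveness should open a discussion about further investment in these modules. A mistaken statement that benefits wear off would feed that discussion and direct follow-up research at a loss that may not have happened.

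**Working it through.** **Inputs from the documents (4.4, 10.1).** Effect size d = 0.5. Test and error rates: "power of .8, a p-value of 5%, and an independent two-sided t-test as method of analysis". Evaluable numbers: 64 per arm, 128 overall. Allowance for loss and recruitment target: "Accounting for a drop-out of 20%, the goal for inclusion is set at a total of 154 patients".

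**Assumptions, not in the documents.** T2–T3 correlation r of 0.5–0.7; between-outcome correlation 0.3 or 0.5; d = 0.3 and 0.4 as sensitivity values; 70 per arm at T2 where unequal visits are examined. For T3, 154 × 0.8 = 123.2, about 61.5 per arm.

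**1. The plan's own figure.** n per arm = 2(1.960 + 0.842)²/0.5² = 62.8, so 63 by the normal approximation. The exact t-test gives 63.8, so 64, as stated. Power at 64 is 80.1% (t) or 80.7% (normal). 128 × 1.2 = 153.6 reproduces 154.

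**2. One outcome, same true effect at T2 and T3.** Each test statistic has mean d√(n/2); at d = 0.5 and n = 64 this is 0.5 × √32 = 2.83. The two statistics correlate at r√(n₃/n₂). Then P(T2 significant, T3 not) = P(T2 significant) − P(both significant). At d = 0.5 with 64 per arm:
- r = 0.5: 0.807 − 0.697 = 0.110
- r = 0.7: 0.807 − 0.722 = 0.085

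| d | 64 per arm at both visits | 70 at T2, 61.5 at T3 |
|---|---|---|
| 0.5 | 8.5–11.0% | 11–14% |
| 0.4 | 12–16% | 16–19% |
| 0.3 | 12–16% | 15–19% |

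At d = 0.3 with 64 per arm, T3 misses in 31–40% of the trials with a significant T2 (0.122/0.396 to 0.160/0.396).

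**3. Whole trial.** Simulation of three outcomes at two visits. The event is at least one outcome significant at T2 and none at T3, since a T3 success on any outcome moves the trial to scenario 4 or better. Ranges cover both sets of visit sizes, at unadjusted 0.05.

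| Lasting effect | False 'not maintained' verdict |
|---|---|
| d = 0.5 on all three | 2–5% |
| d = 0.5 on one, none on the others | 8–14% |
| d = 0.4 on all three | 6–12% |
| d = 0.3 on all three | 12–19% |

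The Bonferroni divisor is not stated. With d = 0.5 on all three, 0.05/3 gives 5–10%. At 0.05/9, with 64 per arm and r anywhere from 0.3 to 0.8, the range is 7–15%.

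**4. Sensitivity to the analysis.** Steps 2 and 3 compare raw visit means. With equal correlation r among T0, T2 and T3, change from baseline divides the mean of the statistic by √(2(1−r)) and sets the correlation to 0.5. Baseline adjustment divides by √(1−r²) and sets it to r/(1+r). For d = 0.5 and 64 per arm:
- change from baseline: 11.0% (r = 0.5), 3.5% (r = 0.7)
- baseline-adjusted: 7.4% (r = 0.5), 2.0% (r = 0.7)

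For d = 0.3 both give 16–20%.

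**5. The direct contrast.** The group effect at T3 minus that at T2 has SE = √(2 × (2/n) × (1−r)) in SD units. At n = 64 this is 0.177 (r = 0.5) or 0.137 (r = 0.7). With equal effects, a 95% CI lies wholly on the side of decline in 2.5% of trials. If the contrast is required in addition to the significant-then-not pattern, the false label at d = 0.5 falls from 8.5–11.0% to between 1% and 2%. Its power for complete loss of d = 0.5 is Φ(0.5/0.177 − 1.96) = 81% or Φ(0.5/0.137 − 1.96) = 95%. For loss of half (0.25) it is 29% or 45%.

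**The case against.** The plan is not silent on change over time. The group-by-time interaction asks whether the arms change differently, and the closing paragraph commits to examining how long changes last. This stands, and it would be wrong to say that the plan contains no test of change. But the overall interaction spans T0–T3 and does not isolate T3 against T2, the within-group tests are not between-group contrasts, and no verdict is tied to either.

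A reader might infer from the per-outcome rates that one trial in ten to one in five would wrongly report fading. The documents do not support that as a general trial rate. Scenario 4 calls the intervention effective on a single T3 success, and at the planned d = 0.5 on all three outcomes that leaves 2–5%. Higher rates need a smaller effect, a single responsive outcome or a strict Bonferroni divisor. Two of these are plausible on the protocol's own account: section 1 reports that therapists expected only a slight strengthening of existing treatment, and section 8.1 says it is unclear which outcome will best show change.

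A reader might also infer that the rule distorts the effectiveness verdict. It does not. That verdict rests on T3 alone, and a null T3 result would still not be called effective after the fix.

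Finally, the correlations and the 70 per arm at T2 are assumptions, and a baseline-adjusted analysis can lower the d = 0.5 rates considerably. This stands too. At d = 0.3 the problem remains under every analysis tried.

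**Conclusion.** The point holds as a gap in the decision rule. Scenarios 2 and 3 state that effects were lost without a between-visit contrast of the group effect. For a truly constant effect, the misleading pattern appears on a given outcome in about 9–11% of trials at d = 0.5 and 12–16% at d = 0.3–0.4, and in 11–14% and 15–19% if T3 is smaller as assumed. The trial-level error is small if all three outcomes respond as planned, and reaches 8–19% if only one responds at d = 0.5 or if all respond at d = 0.3. These figures rest on the assumed correlations, a raw visit comparison and unadjusted 0.05. What is at risk is the durability conclusion and the research agenda attached to it.

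**What to change.** In section 10.1:

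- **Scenario 3.** Allow 'not maintained' only if the T3-minus-T2 group contrast from the planned mixed model shows a decline in benefit with a 95% CI excluding zero. Otherwise report the T3 effect with its CI and state that durability is uncertain.
- **Scenario 2.** Apply the same rule to T2 minus T1, and to T3 minus T1 for the long term.
- **Scenario 4.** Report the three T3 effects with CIs in place of saying that change was absent on the other measures.
- Fix the direction of each contrast in advance so that a positive value means benefit, since improvement in aggression is a fall in score.

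The cost is some wording and a few contrasts per outcome from a model already planned, with no new data. The drawback is limited power for partial loss (29–45% for loss of half of d = 0.5), so 'durability uncertain' will be reported more often. That would be an accurate description of what the trial can show.
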